Studies have shown that the oral health quality of life (OHQoL) is impacted by orthodontic treatment. After orthodontic treatment, studies have shown a significant improvement in OHQoL compared to baseline measures.^{44,45} However, during orthodontic treatment, OHQoL reduces significantly, as has been shown in younger patients.⁴⁶ Motivation measures related to self-empowerment and participation in treatment have been shown to improve the overall OHQoL in schoolchildren.⁴⁷ Limited studies are available regarding the OHQoL during orthodontic treatment and further studies are needed to determine which factors contribute to improving the overall experience for patients successfully completing orthodontic nonextraction treatment with tooth movement .

Study Rationale

Currently, orthodontic treatment typically lasts approximately 2 years. There are a number of advantages for reducing the duration of treatment, including reducing the potential risk of caries², root resorption³ and for minimizing patient “burn out” from prolonged treatment.

While some evidence does exist that vibration may accelerate the speed of tooth movement, the biological mechanism is still unknown. Identification of specific factors involved in tooth movement that are further stimulated by vibration would help to understand the mechanisms involved as well as discover possible biologic targets which could be utilized or modified to maximize the benefits of vibration treatment.

The purpose of this study is to identify novel biological factors that are expressed in patients undergoing orthodontic tooth movement in conjunction with vibration appliance therapy.

Outcome Assessments

- *Primary outcome:* Changes in the expression of salivary biomarkers of bone remodeling
- *Secondary outcomes:* Changes in 1) tooth mobility, 2) change in alignment 3) changes in pain and OHQoL

Hypotheses, aims and objectives

Scientific Hypotheses

- 1) The expression of biological markers of bone remodeling are increased in combined vibration-fixed appliance treatment.
- 2) The degree of tooth mobility is increased in patients undergoing combined vibration-fixed appliance treatment compared to orthodontic treatment alone.
- 3) The percent change in alignment is greater in patients undergoing combined vibration-fixed appliance treatment compared to controls during the first 6 months of treatment.

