- 4) The orthodontic treatment pain will be reduced in patients undergoing combined treatment with a vibration appliance compared to controls.

General Objectives

Few studies exist examining the effect of vibration appliances on the rate of orthodontic tooth movement in patients. Furthermore, there is a great need to better understand the biological mechanisms by which vibration treatment may enhance tooth movement. *The primary objective of this study is to identify potential factors involved in bone remodeling which may be regulated during fixed appliance treatment in conjunction with vibration therapy.*

Specific Aims

[figure not shown]
- 1) To determine if combined vibration-fixed appliance treatment alters the expression of specific bone remodeling factors in saliva compared to fixed orthodontic treatment alone.
- 2) To further elucidate the role of vibration treatment on the degree of tooth mobility during fixed appliance treatment compared to control.
- 3) To determine if combined vibration-fixed appliance treatment increases the speed of orthodontic tooth movement during the alignment phase of treatment.
- 4) To evaluate the role of vibration treatment in the control of pain in patients undergoing orthodontic treatment.

Study Design and Screening Procedures

Study Design: Randomized controlled clinical trial:

N=40 @ UCHC Orthodontic Clinic, enrolled pre-bonding

10 Randomized to each Arm

Screening & Recruitment Procedures

Approximately 600 patients begin treatment every year in the University of Connecticut Orthodontic Clinic. The pilot project aim is to recruit a total of 40 patients, with 20 male and 20 female subjects, equally divided between control and vibration groups (above).. Based on the projected starts, we anticipate meeting the recruitment goals during the first 12 months of the study.

Prospective subjects will be screened for this study after completing all the usual initial screening procedures for patients in the University of Connecticut Orthodontic Clinic with their appointed primary orthodontic provider. The primary orthodontic provider will determine if the adult patient is likely to qualify (pre-screen) for the study based on the inclusion/exclusion criteria. The initial clinical indicators of eligibility evaluated during the pre-screen are a healthy patient undergoing non-extraction treatment with good oral hygiene. Male and female subjects of all ethnicities will be included if between the ages of 15-35 years of age.

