Once recruited to the study and after baseline measures are taken at T0 by the study coordinator, the randomization will be performed. Since study groups will be subdivided by gender, separate randomization will be performed for males and females. Block randomization will be used. Based on gender, 20 opaque envelopes will be generated containing the group allocation (10 for the vibration study group, 10 for the non-vibration control group). At the time of randomization, the

subject will choose an envelope and disclose the group assignment. For subjects allocated to the vibration group, the study coordinator will provide detailed instructions as to how to operate the appliance and will instruct those subjects to use it for 20 minutes per day.

Timetable of Study Assessments

Assessment/ Visit	Screen	Baseline T0	Visit T1	Visit T2	Visit T3
Week	2d-to -6w	0	5-6	10-12	15-17
Consent	X				
Inclusion Criteria/ Confirm	X	X			
Alginate Impression		X	X	X	X
Randomization *		X			
Braces applied /bonded		X			
Vibration Appliance instructions**		X			
Saliva Collection		X	X	X	X
Clinical Data		X	X	X	X
Periotest		X	X	X	X
Pain Diary*** & OHIP 14		X	X	X	X***
Model Analysis		X	X	X	X
Record Adverse Effects		X	X	X	X

*Randomization before bonding

**For vibration group only- SC initially provides device and manufacturer's instructions.

*** Diary provided @ Baseline & visit T1, T1 to be collected on next visit.

III. Data Collection Procedures (See Study Timetable)

On the day of bonding (T0), prior to the placement of any appliances, baseline unstimulated whole saliva will be collected and Periotest will be performed on selected teeth in the mandibular arch. In addition, alginate model impressions will be taken. These procedures will be described in more detail in the next sections. Once baseline measures have been taken, the PI will perform the randomization and notify the study coordinator as to which group the subject is assigned to ("vibration treatment" or "no vibration"). The patients allocated to the vibration treatment group

will be provided with the AcceleDent appliance and instructed to use the 20 minutes per day according to the manufacturer's instructions.

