(the study coordinator) will collect all tooth mobility measurements with the Periotest and means will be evaluated using non-parametric statistical analyses.

A Wilcoxon Rank Sum test for independent samples will be used to assess differences between groups for all the continuous variables with an $\alpha=0.05$ for irregularity index changes-Periotest measurements, VAS & OHIP-14 measures.

Salivary biomarker expression will be analyzed by ANOVA to assess differences between the four study groups at each time point. The study coordinator and principal investigator will perform statistical analyses.

VII. Timetable Table Timeline of Performance Goals:

Activity	Year 1-2014			Year 2-2015		
	X					
IRB, Staff training & preparation	X					
Subject Recruitment & Enrollment	X	X	X			
Final Assessments/Endpoints (17 weeks)				X		
Data Entry & Cleaning				X	X	X
Data analyses					X	X
Report writing						X

Expected Start Date: 2/1/2014

General Time Table

January 2014

Submit IRB for full board review

February 2014

Enrollment begins

Begin data collection for T0 time point in recruited subjects

August 2014

Initially recruited subjects complete study to final endpoint (T4)

June 2015

All consented subjects will have completed study

Data collection complete (N=20)

July 2015

Data analyses conducted

August 2015

Manuscript Preparation

➤ ***Expected Completion Date:*** August 2015

5) **Budget**

Patients will be responsible for covering the cost of orthodontic treatment in the University of Connecticut Orthodontics Clinic (either directly or with insurance). However, a deduction of \$400.00 on the standard orthodontic fees will be given to every patient enrolling in the research. The participants will receive this incentive in the form of \$100.00 at each research appointment completed until the maximum benefit is reached. If a participant is not compliant with the study protocol, he/she will be dismissed from the study and will not receive any further compensation. The same orthodontic procedures will be used for all subjects in this study regardless of study group.

Please see the attached budget detailing the study-specific costs.

6) **Dissemination**

The results of this research will be published in a peer-reviewed dental journal. In addition, this work is likely to be presented at national/international meetings.

References

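### The only biomarker analysis is a four-group ANOVA at each visit: it names no vibration-versus-control test and, as worded, leaves T0 out of the follow-up comparisons

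*Combined protocol and SAP*

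**What the plan says.** Under Outcome Assessments, the primary outcome is "Changes in the expression of salivary biomarkers of bone remodeling". Section IV (Sample size and justification) repeats that it is a change. Specific Aim 1 is a two-arm question: "To determine if combined vibration-fixed appliance treatment alters the expression of specific bone remodeling factors in saliva compared to fixed orthodontic treatment alone". No aim or hypothesis concerns sex.

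Section II (Randomization Procedures) stratifies by sex: "Since study groups will be subdivided by gender, separate randomization will be performed for males and females". Each sex has 20 envelopes, 10 per arm. Section IV describes a pilot of 40 patients in four groups formed by sex and arm.

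Section III (Data Collection Procedures) has the T0 sample taken early: "prior to the placement of any appliances, baseline unstimulated whole saliva will be collected". Allocation follows: "Once baseline measures have been taken, the PI will perform the randomization". Saliva is collected again at T1, T2 and T3.

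The biomarker analysis in section VI is one sentence: "Salivary biomarker expression will be analyzed by ANOVA to assess differences between the four study groups at each time point". The sentence before it reads "A Wilcoxon Rank Sum test for independent samples will be used to assess differences between groups for all the continuous variables", but the measures it then lists are "irregularity index changes-Periotest measurements, VAS & OHIP-14 measures". Biomarkers are not among them.

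**The concern.** The Wilcoxon sentence cannot be borrowed to supply a two-arm biomarker test: its list omits the biomarkers, and the next sentence gives them a different method. The ANOVA sentence therefore has to carry Aim 1, and it has two gaps.

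- **No arm comparison is named.** A comparison of four sex-by-arm cells has 3 degrees of freedom and responds to sex, to arm and to their interaction. Sex is not randomised. A significant result would not by itself show an effect of vibration, and an effect of similar size in both sexes is diluted over three degrees of freedom. If a two-way sex-by-arm ANOVA is meant, it contains an arm effect, but the plan does not say that this effect answers Aim 1.
- **T0 is not used in the follow-up tests.** The visits tested include T0, where no change can exist, so the natural reading is a separate comparison of levels at each visit. The outcome is worded as change, and every patient gives a T0 sample, yet nothing brings it into the T1 to T3 tests.

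The trial is a pilot, and section IV says that no randomised trials exist to predict the effect. Clear estimates of the arm effect are then the main thing it can deliver.

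**Working it through.** **What can be reproduced.** The sample size is design arithmetic: 4 cells × 10 = 40, as stated. The plan gives no power, effect size, SD or T0-to-follow-up correlation, so there is no power figure to reproduce.

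**Inputs.** From the documents: 10 per sex-by-arm cell. Assumed: one marker at one visit, effects in SD units, correlation r between T0 and the visit, all 40 patients completing, and alpha 0.05. Section VI attaches alpha only to the Wilcoxon measures.

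**Step 1: four-group test against arm effect.** With n per cell, the noncentrality is λ = n × (sum of squared deviations of the cell means). For an arm effect d equal in both sexes, the cell means lie at ±d/2, so λ = 10 × 4 × (d/2)² = 10d². Both tests have this λ, but the four-group test uses F(3, 36) and the arm effect in the two-way layout uses F(1, 36).

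| d | λ | Four-group test | 1-df arm effect |
|---|---|---|---|
| 0.5 | 2.5 | 21% | 34% |
| 0.8 | 6.4 | 50% | 69% |
| 1.0 | 10.0 | 71% | 87% |

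At d = 0.8 the difference is 69 − 50 = 19 points.

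**Step 2: sex difference only.** With no vibration effect and a sex difference s in levels, λ = 10s². The four-group test is then significant in 21%, 50% and 71% of trials for s = 0.5, 0.8 and 1.0, exactly as often as for a vibration effect of the same size. The arm test stays at 5%.

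**Step 3: adding T0.** Power for d = 0.8 in both sexes. The ANCOVA has arm, sex and T0 (1 and 36 df) and was simulated so that chance T0 imbalance is included. The change-score arm test has λ = 6.4 / [2(1 − r)], because a change has variance 2(1 − r).

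| r | ANCOVA arm effect | Against 69% without T0 | Change-score arm test |
|---|---|---|---|
| 0 | 68% | −1 | 41% |
| 0.2 | 70% | +1 | 50% |
| 0.3 | 72% | +3 | 55% |
| 0.5 | 80% | +11 | 69% |
| 0.7 | 92% | +23 | 89% |

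**Step 4: fewer completers.** Section V disqualifies patients who miss a visit window. With 8 per cell (32 patients) and d = 0.8, λ = 8 × 0.64 = 5.12. Power is 40% for the four-group test and 59% for the arm effect. With T0 it is 57%, 59%, 61%, 70% and 85% at r = 0, 0.2, 0.3, 0.5 and 0.7.

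**Step 5: where the four-group test does better.** Take a 1.2 SD effect in one sex only. One cell mean is shifted, so the sum of squares is 1.44 × 3/4 = 1.08 and λ = 10.8. The four-group test has 75% power. The ANCOVA without an interaction has 41%, 44%, 51% and 66% at r = 0, 0.3, 0.5 and 0.7.

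**The case against.** The strongest reply is that the figures in steps 1 and 2 assume the ANOVA is run on levels. The outcome is worded as change. If the analysed value is change from T0, a sex difference already present at T0 cancels, and the four-group test rejects about 5% of the time, not 50% or 71%. Its power for a 0.8 SD effect would then be 26%, 37%, 50% and 74% at r = 0, 0.3, 0.5 and 0.7. This is right, and the sex-only figures should be read as conditional on levels. It does not rescue the sentence, which refers to expression at each time point, although the sentence before it speaks of changes for irregularity. On the change reading an arm comparison is still not named.

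Second, the same ANOVA at T0 would often flag a stable sex difference, and the cell means would show whether the groups split by sex or by arm. That is a useful informal check, but it does not define a test. The documents give no evidence that any marker differs by sex, so the sex-only figures are illustrations.

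Third, T0 adjustment is only a gain in precision, and a negligible one for r up to 0.3. This stands: arms are randomised within sex, so comparing levels is unbiased. Naming the arm effect in a two-way ANOVA would by itself bring the 19 points.

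Fourth, the four groups are a deliberate design choice, and an overall arm test loses power when the effect is confined to one sex. This also stands (step 5). But Aim 1 asks about vibration overall, and no aim concerns sex.

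Finally, pilot status excuses the missing power calculation. It does not excuse leaving the primary comparison undefined.

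**Conclusion.** The concern holds and should be fixed. That no vibration-versus-control test is named for the biomarkers follows directly from the text. That T0 is left out of the T1 to T3 tests is the natural reading, though not the only possible one.

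Under the assumptions listed, the four-group test on levels gives up about 19 points of power for a 0.8 SD effect common to both sexes, and it cannot separate vibration from sex. Using T0 changes power by −1 to +23 points as r runs from 0 to 0.7. If a two-way ANOVA is intended, the power loss disappears and what remains is that the deciding effect is not named. No bias in the arm comparison is claimed.

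**What to change.** Replace the biomarker sentence in section VI with:

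*For each biomarker, Aim 1 is tested by the 1-df vibration-versus-control effect at each follow-up visit (T1, T2, T3), from an ANCOVA with arm, sex (the randomisation stratum) and that marker's T0 value. The arm-by-sex interaction is exploratory. T0 values are described by group, and no treatment inference is drawn from them.*

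One repeated-measures model over T1 to T3 with the same terms is equally acceptable, provided it states whether the arm effect is taken per visit or averaged.

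**Cost.** Only the analysis wording changes. Arm, sex and the T0 to T3 saliva values are already collected, so no patients, visits or assays are added. The statistical price is about one point of power if T0 is uncorrelated with follow-up, and lower power for an effect in one sex only: in the 1.2 SD example, 44%, 51% and 66% at r = 0.3, 0.5 and 0.7, against 75%.

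**What this leaves open.** It settles which test answers Aim 1 for a given marker and visit. It does not settle which marker or visit decides, or how to handle 14 markers (13 listed targets plus CTX) × 3 visits = 42 tests. That is a separate matter.
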